Basic Information

1. * Title of study:

Impact of Theraworx Foam on Pain and Motion and Patient-Reported Outcomes in Thumb Arthritis

2. * Short title:

Theraworx Foam

3. * Brief description:

Thumb carpometacarpal osteoarthritis (CMC OA) affects up to 33% of people over the age of 40, which leads to inflammation, pain, and weakness of the CMC joint.

Treatment modalities are both conservative and surgical with surgical options including osteotomy,

bone excision, ligament reconstruction, and various prosthetic implants. The conservative treatment options, however, are limited to NSAIDs and bracing or steroid injections.

Advances in topical therapies have the potential to deliver focused treatment to the CMC joint. Novel treatment of inflammation can potentially reduce inflammation and pain associated with progressing osteoarthritis. Theraworx Relief is an FDA registered foam that has theoretical impact on inflammation reduction in human subjects treated with the topical foam.

This pilot study seeks to investigate potential benefit in the use of Theraworx Foam in patients diagnosed with thumb CMC OA. Patients presenting to our upper extremity orthopedic surgery clinic for thumb/hand/wrist pain will be diagnosed by a Board Certified Hand

Surgeon as per standard protocols. Patients who are recommended to follow a conservative treatment modality and are interested in participating in this study will be randomized into treatment or control groups. Both groups will undergo symptom assessment, strength testing, and range of motion testing prior to starting the

standard

conservative treatment of bracing. The treatment group will use the TheraWorx topical foam and the compression wrap nightly for 2 weeks for at least 6 hours per night. Control group will use a compression wrap for the same time period. Both groups will return at 1 and 2 weeks for repeat strength and range of motion testing and symptom assessment.

4. * Principal investigator:

[name]

5. * Does the investigator have a financial interest related to this research?

Yes No

6. * Will an external IRB act as the IRB of record for this study?

Yes No

7. * What kind of study is this?

Single-site study

8. Attach the protocol:

- Sponsor/Multicenter protocol
- Investigator-initiated protocol
- Emergency Use Consent/ Protocol/ FDA Form 3926
- [Exempt Application form](#)

Document Category Date Modified Document History

There are no items to display

Study Aims

1. * Describe the purpose, specific aims, or objectives and state the hypotheses to be tested:

The purpose of this study is to assess the efficacy of Theraworx foam in reduction of inflammation and pain as measured by subjective pain/disability scales, motion, and strength testing.

Specific Aim 1: To assess the efficacy of Theraworx foam in reduction of pain on subjective pain/disability scales for thumb CMC arthritis.

- Hypothesis 1a: Patients given the Theraworx foam and compression wrap will see significant improvements in reported Numeric Pain Rating Scale (NPRS) compared to patients who are given the placebo foam and compression wrap and Theraworx foam alone.
- Hypothesis 1b: Patients given the Theraworx foam and compression wrap will see significant improvements in score on the Disabilities of the Arm, Shoulder, and Hand (DASH) questionnaire compared to patients who are given the placebo foam and compression wrap and Theraworx foam alone.

Specific Aim 2: To assess the efficacy of Theraworx foam to improve function and patient reported outcomes for thumb CMC arthritis.

- Hypothesis 2a: Patients given the Theraworx foam and compression wrap will see significant improvements wrist range of motion compared to patients who are given the placebo foam and compression wrap and Theraworx foam alone.
- Hypothesis 2b: Patients given the Theraworx foam and compression wrap will see significant improvements in grip and pinch strength compared to patients who are given the placebo foam and compression wrap and Theraworx foam alone.

2. * Describe the relevant prior experience and gaps in current knowledge including preliminary data. Provide for the scientific or scholarly background for, rationale for, and significance of the research based on existing literature and how it will add to existing knowledge:

Recent research surrounding the structure and function of the outermost layers of

skin have provided insights into potential avenues for improved health. The skin, primarily the stratum corneum was conventionally described as a biologically inert layer, comprised of keratin and dead epidermal cells. The scientific understanding of the stratum corneum has evolved to see a more dynamic and critical structure to skin health. This barrier has a major role in inflammatory regulation of underlying skin, barrier protection from infection and maintenance of superficial pH that modulates bacterial flora growth and sweat loss.(5,6) Stratum corneum health allows for a multitude of protective functions. The stratum corneum maintains skin pH at approximately 5.0, which allows for healthy flora to exist and deters pathogenic flora colonization. Exogenous rise in skin pH or psychological stress, impacts the skin function, including inflammatory cascade modulation.(7) This is where investigation of agents that maintain stratum corneum integrity can impact the health and physiologic functions of the skin in patients with inflammatory disease.

The need for improved conservative treatment approaches to thumb CMC OA is increasing with increased population longevity and increased rates of OA in younger populations.(8) The Theraworx topical agent is an FDA-registered product and received approval for commercial labelling. The use of plant extracts in Theraworx, such as Aloe Vera, makes it a potent moisturizing agent, but the extracts in Theraworx also have antiinflammatory and pain reducing effects. Allantoin, which has been used in cosmetic preparations for many years, moisturizes by increasing the water content and enhancing health of the upper layers of dead skin cells, helping improve wound healing and injuries of the skin. Beta-Glucan 1,3D is a complex carbohydrate that has been demonstrated to enhance the effectiveness of inflammatory responses within the skin and subcutaneous tissue. These components have potential to impact acute inflammatory responses and promote more rapid healing than non-treatment. (5,6) Previously completed studies on Theraworx foam have shown no allergic reaction at all in all patients as well as being a non-irritant for all patients. (9)

Significance: If the Theraworx foam and/or Theraworx foam with compression wrap can be shown to reduce pain and allow for improved functional measures, the product can be proposed as an option for conservative treatment of thumb CMC OA and reduce the reliance on oral pain medications, steroid injections, and surgery.

Study Design

1. Total number of subjects to be enrolled at this site (enter -1 for chart reviews, banking, registries):

60

2. Describe and explain the study design:

After informed consent, subjects will be randomized to one of three groups:

1. Theraworx foam with compression wrap
2. Placebo foam with compression wrap
3. Theraworx foam alone

Baseline testing will include Numeric Pain Rating Scale (NPRS). The Disabilities of the Arm, Shoulder, and Hand (DASH) will be administered to the participant by the study coordinator. Static range of motion will be tested with a wrist goniometer measuring flexion, extension, ulnar deviation, and radial deviation with the participant's elbow supported on a hand table. Strength testing will be performed with a hand dynamometer and pinch meter. These questionnaires/tests will be performed at baseline, 1 week, and 2 week visits. They should take approximately 10 minutes to complete.

Subjects will be instructed to apply the foam every night (two pumps and rub into the base of the thumb). This will be demonstrated by the research coordinator (to be hired and added to this IRB application).

Participants will be asked to apply the foam nightly for a minimum of 6 and maximum 10 of hours and avoid use of lotions, topical creams, or topical NSAIDs during the study period. Subjects will be advised to avoid other oral prescription or OTC pain relief medications during the 2-week study period. A study data sheet will be given at this time for the participant to document nightly compliance hours, daily Tylenol use, and daily pain rating. This sheet will be collected at the 2 week visit. This portion of the research visit should take approximately 5 minutes but will allow for time for questions.

Randomization will occur via block randomization designed to randomize subjects into groups that result in equal sample sizes.

3. Describe the primary and secondary study endpoints:

All endpoints are primary:

1. Numeric Pain Rating Scale
2. Disabilities of the Arm, Shoulder, and Hand (DASH)
3. Pinch strength
4. Grip strength
5. Thumb range of motion

4. Provide a description of the following study timelines:

Duration of an individual subject's active participation:

2 weeks

Duration anticipated to enroll all subjects:

1 year

Estimated date for the investigator to complete this study (complete primary analyses):

9/30/2019

5. List the inclusion criteria:

Patients of [name], the PI, with the following:

1. Thumb CMC arthritis
2. greater than or equal to age 18
3. Interested in non-operative treatment of thumb arthritis

6. List the exclusion criteria:

1. Recent corticosteroid injection into the thumb joint
2. Non-English speaking
3. skin lesions or rashes on the thumb
4. current use of topical anti-inflammatory medications
5. concomitant thumb/wrist diagnoses that would impact the results (as determined by the PI)
6. known allergy to magnesium

7. Will children or any gender, racial or ethnic subgroups be explicitly excluded from participation?

Yes No

* Identify the subgroups and provide a justification:

Children - arthritis of the thumb CMC joint does not typically exist in subjects less than the age of 18 and including a rare patient that might have CMC arthritis would bias our results.

8. Describe the power analysis used and cite your method of statistical analysis. If a power analysis is not possible, thoroughly justify the sample size required for the study, including appropriate literature citation (alternatively provide page reference in attached protocol):

The mean pain reported in subjects with CMC arthritis is 5 (out of 10) on the numeric pain rating scale. Assuming a clinical meaningful change in pain of 2 on this scale, an alpha of 0.05 and beta of 0.2, the power analysis demonstrates 16 subjects required per group. Assuming a drop out rate of 20%, we will enroll 20 subjects per group.

Research Activities

- 1. * Provide a detailed description of all research activities (including screening and follow-up procedures) that will be performed for the purpose of this research study. This description of activities should be complete and of sufficient detail to permit an assessment of associated risks.**

Screening and Enrollment: Patients diagnosed with thumb CMC OA by the PI and recommended for participation in the study will be assessed for inclusion and exclusion criteria appropriateness by the study coordinator. If they are candidates, consent will be obtained by the PI in a private room and they will be randomized into treatment or control group by the coordinator. At this time, the x-ray taken during routine care by the PI for diagnosis will be obtained and graded for severity.

Demographic information including age and gender will also be collected.

Research Visits: Baseline, 1 week and 2 week visits

Study procedures will be performed by the study coordinator in a patient room equipped with a hand table, if necessary, patient will be moved to an procedure room similarly equipped. Numeric Pain Rating Scale (NPRS), and Disabilities of the Arm, Shoulder, and Hand (DASH) will be administered to the participant by the study coordinator. Static range of motion will be tested with a wrist goniometer measuring flexion, extension, ulnar deviation, and radial deviation with the participant's elbow supported on a hand table. Strength testing will be performed with a hand dynamometer and pinch meter. These questionnaires/tests will be performed at the baseline, 1 week and 2 week visits. They should take approximately 10 minutes to complete. Study coordinator will also provide the participant with the foam and compression wraps and provide instructions for its use. The compression wrap is a cloth wrap (similar to an elastic bandage wrap) that will be saturated/treated with the Theraworx foam. Participants will be asked to apply the foam treated wrap nightly for a minimum of 6 and maximum 10 of hours and avoid use of lotions, topical creams, or topical NSAIDs during the study period. A study data sheet will be given at this time for the participant to document nightly compliance hours, daily Tylenol use, and daily pain rating. This sheet will be collected at the 2 week visit. This portion of the research visit should take approximately 5 minutes but will allow for time for questions.

- 2. Upload a copy of all materials used to collect data about subjects: (Attach all surveys, interview/focus group scripts, and data collection forms except for case report forms, SCID or KSADS):**

Data

Collection

10/9/2018 History

Data

Collection

10/9/2018 History

Data

Collection

9/30/2018 History

3. * Will blood samples be obtained for research purposes? Yes No

Data Safety and Monitoring

- 1. * Describe your plan to periodically evaluate the data collected regarding both harms and benefits to determine whether subjects remain safe. The plan might include establishing a data monitoring committee and a plan for reporting data monitoring committee findings to the IRB and the sponsor:**
The primary investigator will monitor confidentiality and data on a monthly basis to ensure accuracy and recruitment of subjects. Monthly meetings, with the study coordinator will be held to verify compliance and testing procedures. These meetings will monitor recruitment, retention, data, adverse events, and breaches in confidentiality.

The investigators will comply with the IRB's policies for the reporting of serious and unexpected adverse events as addressed in Chapter XVII of the IRB Policies and Procedures Manual.

At the time of the IRB renewal, the PI will submit in writing the information about the frequency of the monitoring, the dates that the weekly meetings took place, a summary of the cumulative adverse events, external factors or relevant information that might have an impact on the safety or ethics of the study, and final conclusion regarding changes to the anticipated risk/benefit ratio to study participation and final recommendations related to the continuation, changing, or termination of the study. Also, at the time of the IRB annual renewal, reported documentation over the past year will be submitted to the IRB.

- 2. * Describe your plan for sharing data and/or specimens:**

Though we currently do not have plans to share data/documents to external persons, if at a future time we wish to share information appropriate approvals will be obtained.

- 3. If any research data is collected, stored, or shared in a paper format, address what precautions will be used to maintain the confidentiality of the data:**

Paper-based records will be kept in a locked filing cabinet and only be accessible to personnel involved in the study. Computer-based files will only be made available to personnel involved in the study through the use of access privileges and passwords and stored on an encrypted /firewall protected network.

Risk and Benefits

1. * Enter all reasonably foreseeable risks, discomforts, hazards, or inconveniences to the subjects related to subjects' participation in the research:

Research Activity	Strength Testing
Common Risks	No Value Entered
Infrequent Risks	Isometric strength testing may result in muscle cramping, discomfort, or fatigue, although occurrence is rare (occurs in less than 1% of people).
Other Risks	No Value Entered

Research Activity	Randomization
Common Risks	Those being randomized to the placebo may not receive direct benefit compared to those randomized to foam.
Infrequent Risks	No Value Entered
Other Risks	No Value Entered

Research Activity	Use of Foam
Common Risks	No Value Entered
Infrequent Risks	Skin irritation, allergic reaction
Other Risks	No Value Entered

Research Activity	Storage of Research Data
Common Risks	No Value Entered
Infrequent Risks	Breach of Confidentiality
Other Risks	No Value Entered

Research Activity	Range of Motion Testing
Common Risks	No Value Entered
Infrequent Risks	The range of motion procedures may result in soreness, however it is rare (occurs in less than 1% of people).

2. * Describe the steps that will be taken to prevent or to minimize risks:

Subject research records will be double-locked, with access only by research personnel listed. Electronic files will be stored in password protected systems. Subject research records and the data linking file will be destroyed after 7 years to decrease the risk of confidentiality being breached.

Subjects will be instructed to not exert themselves in a manner that will cause pain during the procedures. Those who experience any pain or discomfort during the testing procedures will be given the opportunity to rest or terminate the testing session.

Subjects with any prior adverse reactions to topical agents will be excluded. In the event of any adverse event or injury, the investigator will provide the subject for proper medical treatment.

3. Financial risks - will the subject or insurer be charged for any research required procedures?

Yes No

4. Describe the steps that will be taken to protect subjects' privacy:

Examination and testing will be completed in a private examination room

5. What steps will be taken in the event that a clinically significant, unexpected disease or condition is identified during the conduct of the study:

The PI will notify the patient and either treat the condition or provide an appropriate referral.

6. Describe the potential benefit that individual subjects may experience from taking part in the research or indicate if there is no direct benefit. Do not include benefits to society or others:

There may be a direct benefit for participating in this study, if the study hypothesis is true, there is a chance that the treated wrap will provide more pain relief and inflammation reduction than the placebo wrap/bracing alone.

The data gathered will allow us to determine if there is a benefit to the test foam in reducing pain and inflammation in thumb

CMC OA. Having an understanding of the product in recovery may lead to future studies that investigate a wider array of measures related to conservative CMC OA treatment.

7. Do you anticipate any circumstances under which subjects might be withdrawn from the research without their consent?

Yes No

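### Foam + wrap versus foam alone cannot be masked as to foam and tests the wrap, so it should not be a condition for concluding that the foam works on pain or DASH

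*Combined protocol and SAP*

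**What the plan says.** Study Design, item 2 states that "subjects will be randomized to one of three groups". The first is Theraworx foam with a compression wrap. The other two are "2. Placebo foam with compression wrap" and "3. Theraworx foam alone". No group receives placebo foam without a wrap.

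Specific Aim 1 concerns the efficacy of the foam on scales that the protocol itself calls subjective. Hypothesis 1a expects foam + wrap to do better on "reported Numeric Pain Rating Scale (NPRS) compared to patients who are given the placebo foam and compression wrap and Theraworx foam alone". Hypothesis 1b names the same two comparators for DASH. Neither ranks one comparator above the other.

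The Statistical Analysis Plan names pain at 2 weeks as primary and specifies ANOVA at 0.05 for every outcome. It names no pairwise contrast.

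No section mentions blinding, matched foams or coded labels. Risk and Benefits, item 1 (Randomization) says only: "Those being randomized to the placebo may not receive direct benefit compared to those randomized to foam". Research Activities, item 1 has the coordinator randomize, hand out the foam and wraps, and administer the NPRS and DASH.

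**The concern.** In this design the absence of a wrap reveals the foam. A participant who knows the arms and goes home without a wrap can deduce that the foam is active. Coding the foams or masking the coordinator cannot prevent this, because it follows from the arm list. The outcomes in Hypotheses 1a and 1b are the participant's own ratings, which expectation can move.

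The same contrast has a second weakness. Foam is present in both arms, so the difference between them is the effect of adding a wrap. It nevertheless stands as an equal half of two hypotheses under an aim about the foam. Effective foam could be reported as failing Hypothesis 1a because the wrap adds little, or because expectation differed between an arm with a wrap and one without.

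**Working it through.** **What each contrast estimates.** Let F be the foam effect, W the wrap effect (taken as additive) and e the expectation response in an arm. Mean improvement is:

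- foam + wrap (A): F + W + e_A
- placebo foam + wrap (B): W + e_B
- foam alone (C): F + e_C

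| Contrast | Estimates | Can foam identity be masked? |
|---|---|---|
| A − B | F + (e_A − e_B) | Yes, if the foams are matched and coded (not stated) |
| A − C | W + (e_A − e_C) | No, C is revealed by the missing wrap |
| C − B | F − W + (e_C − e_B) | No, same reason; foam and wrap both differ |

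Only A − B isolates the foam. C − B also feeds the overall ANOVA.

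**Descriptions of the control, side by side.**

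| Place | What it describes |
|---|---|
| Basic Information, item 3 | Two groups; the control uses a wrap and no placebo foam is mentioned |
| Study Design, item 2 | Three groups; placebo foam with wrap; foam rubbed into the thumb base |
| Research Activities, item 1 | Treatment or control group; the wrap is saturated with Theraworx foam |
| Risk and Benefits, item 6 | A treated wrap compared with a placebo wrap or bracing alone |

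These cannot all describe one trial, and none says who is masked.

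**The plan's sample size.** Study Design, item 8 gives a difference of 2, alpha 0.05, power 0.80 and 16 per group, but no SD. With the two-sided normal formula and an assumed SD of 2.0, n = 2 × [2.0 × (1.960 + 0.842) / 2]² = 15.7, so 16. Any SD from 1.956 to 2.019 gives 16. Then 16 / 0.8 = 20 and 3 × 20 = 60, as stated.

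**No bias, foam works, wrap adds nothing.** Take F = 2, W = 0 and equal expectation. Improvements are A = 2, B = 0, C = 2. At SD 2.0 and 16 per arm:

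- A − B = 2. Noncentrality 2 / (2.0 × √(2/16)) = 2.83, pooled df 45, power 79%.
- A − C = 0. It is significant in the hypothesised direction 2.5% of the time.
- The ANOVA rejects about 81% of the time. The means (2, 0, 2) have the same spread as (2, 0, 0).

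The foam would probably be detected, while the foam-alone half of Hypothesis 1a would almost always fail.

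**Expectation gap, illustration only.** Assume a true wrap benefit of 2 on top of foam and a gap b = |e_A − e_C|. Power comes from the noncentral t with noncentrality (2 ∓ b) / (SD × √(2/16)), df 45, two-sided 0.05. At SD 2.0:

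| b (points) | Favours foam alone (2 − b) | Favours foam + wrap (2 + b) |
|---|---|---|
| 0 | 79% | 79% |
| 0.25 | 68% | 88% |
| 0.5 | 55% | 93% |
| 1.0 | 28% | 99% |

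With b = 0.5 against foam + wrap, power falls from 96% to 79% at SD 1.5 and from 60% to 38% at SD 2.5. The documents give neither the SD, nor b, nor a wrap effect. The protocol's 2 points is a meaningful change in pain, not a wrap benefit.

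**The case against.** A reader might infer that the foam-alone arm biases this comparison against the hypothesis, because its participants know their foam is real while wrap participants must guess. The documents do not support that, for three reasons.

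- **Masking in the wrap arms is unknown.** If the foam is open, or the control is a wrap with no foam, participants in both foam arms know they have active foam. That particular gap then disappears and a wider lack of blinding takes its place.
- **What participants are told is inferred.** The consent pages are not available. The risk entry shows that a placebo exists, not that participants learn it comes only with a wrap. Disclosure is likely, since consent precedes randomization, but it is not shown.
- **Direction is unknown.** Certainty of active foam would help foam alone. Visibly lacking a wrap could hurt it, particularly as Risk and Benefits, item 6 presents the treated wrap as the source of benefit.

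It can also be said that the SAP plans only ANOVA, so the disputed pairwise test is not strictly in the plan. That stands, but the hypotheses still name the comparison, and the Significance paragraph would propose the product on results for foam with or without the wrap.

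A reader might further infer that earlier users would recognise the placebo, because the product has commercial labelling. Nothing describes the placebo's properties or shows that earlier use is common, so this is no ground for the point. A treatment-guess question would not settle it either: the answer is confounded with perceived benefit and changes no result.

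What survives is that foam identity cannot be hidden in the foam-alone arm from a participant who knows the arms, and that the contrast does not test the foam.

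**Conclusion.** The point holds as a risk of bias and a mismatch between aim and contrast, not as a demonstrated bias. Two parts follow from the arm list: wrap-free participants always have active foam, and foam + wrap versus foam alone measures the added wrap. Working foam can therefore fail that half of Hypotheses 1a and 1b even with perfect masking. The expectation component depends on participants knowing the arms and on undescribed masking; its sign and size are unknown. The power range above (55% to 93% around 79% for a 0.5-point gap) rests on an assumed SD of 2.0, an assumed gap and an assumed 2-point wrap benefit. It shows sensitivity and is not an estimate. Foam alone versus placebo foam + wrap carries the same masking problem and also mixes foam with wrap, so a significant overall ANOVA does not by itself answer the foam question.

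**What to change.** 1. In Hypotheses 1a and 1b and in the Statistical Analysis Plan, base the conclusion that the foam reduces pain or disability on foam + wrap versus placebo foam + wrap, named as a contrast.
2. Label foam + wrap versus foam alone as unmasked and supportive, addressing what the wrap adds to the foam. State that success on it is not required for the foam conclusion.
3. Reconcile Basic Information item 3, Study Design item 2, Research Activities item 1 and Risk and Benefits item 6 on what the control receives. State whether the foams are masked, for whom and how. If the reconciled control has no placebo foam, the contrast in step 1 must be re-described, because it would not be masked either.

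These are wording changes that need no extra participants or visits. The cost is that the wrap comparison on pain and DASH becomes supportive. A placebo-foam-alone arm would also separate foam from wrap, but at 20 per group it raises enrolment from 60 to 4 × 20 = 80; the wording change does not need it.

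### One coordinator role allocates, dispenses and assesses with no masking described, and the SAP's three-arm ANOVA does not isolate the contrast that tests the foam

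*Combined protocol and SAP*

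**What the plan says.** Research Activities, item 1, assigns these tasks to one role, the study coordinator:

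- Eligibility: patients "will be assessed for inclusion and exclusion criteria appropriateness by the study coordinator".
- Allocation: after consent by the PI, "they will be randomized into treatment or control group by the coordinator".
- Dispensing: "Study coordinator will also provide the participant with the foam and compression wraps and provide instructions for its use".
- Questionnaires: "Numeric Pain Rating Scale (NPRS), and Disabilities of the Arm, Shoulder, and Hand (DASH) will be administered to the participant by the study coordinator".
- Physical tests: "Study procedures will be performed by the study coordinator in a patient room equipped with a hand table". The sentences on goniometry, grip and pinch name no tester, but this opening sentence covers them.

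Assessments take place at baseline, 1 week and 2 weeks, so two of the three follow allocation and dispensing.

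Study Design, item 2, lists three arms: Theraworx foam with wrap, "Placebo foam with compression wrap" and "Theraworx foam alone". On allocation it says only: "Randomization will occur via block randomization designed to randomize subjects into groups that result in equal sample sizes". Block size, the holder of the list and concealment are not given. Item 3 lists five endpoints and calls all of them primary.

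Study Aims, item 1, Hypotheses 1a to 2b, compare Theraworx plus wrap with placebo plus wrap and with foam alone. The Statistical Analysis Plan makes VAS pain at 2 weeks primary (taken here as the same measure as the NPRS), analyses it and the secondary outcomes by ANOVA at 0.05, and names no contrast.

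**The concern.** There are two linked weaknesses.

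The first is ascertainment. A person who makes the allocation and hands over the wraps knows who is in the foam-alone arm, and so does the participant. Grip, pinch and goniometry depend on encouragement, positioning and reading, so knowledge of the arm can reach the result directly. Pain and DASH are self-reported. For them the route is indirect: administration by the coordinator, and the participant's knowledge of having a wrap or not. A placebo foam suggests that masking between the two wrap arms was intended, but no described step delivers it.

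The second is the analysis. A three-arm ANOVA asks whether any arm differs. The foam-alone arm differs from the others in two ways that have nothing to do with the foam: it is recognisable, and it lacks the wrap. Either could produce a significant test with an inert foam. The Significance paragraph before Study Design would propose the product as a treatment option if foam, with or without wrap, is shown to work, so a significant ANOVA could be read as support for the foam.

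**Working it through.** **1. Exposure, counted from the documents.** Of five endpoints, three are measured by the coordinator (pinch, grip, motion) and two are administered by the coordinator (NPRS, DASH): 5 of 5. One of three arms is recognisable: 20 of 60 planned participants.

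**2. The plan's sample size.** Study Design, item 8, gives a difference of 2 points, alpha 0.05, beta 0.2 and 16 per group, but no SD. With an assumed SD of 2, the two-sided normal formula gives n = 2 × (1.960 + 0.842)² × 2² / 2² = 15.7, so 16. Dropout: 16 / (1 − 0.2) = 20 per group, and 3 × 20 = 60. The calculations below use 16 per arm.

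**3. False-positive rate of the three-arm ANOVA (illustration).** Assume an inert foam and a shift of d SD in the foam-alone arm only. With arm means 0, 0, d, the squared deviations sum to (2/3)d², so the noncentrality is 16 × (2/3)d², with 2 and 45 degrees of freedom.

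| Assumed shift | d | Noncentrality | P(ANOVA p < 0.05) |
|---|---|---|---|
| none | 0 | 0 | 0.050 |
| 0.5 points, SD 3 | 0.167 | 0.30 | 0.071 |
| 0.5 points, SD 2 | 0.25 | 0.67 | 0.100 |
| 0.5 points, SD 1.5 | 0.333 | 1.19 | 0.143 |

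A simulation at d = 0.25 (200,000 runs) gave 0.099 for the ANOVA, 0.107 for Theraworx plus wrap versus foam alone, and 0.049 for Theraworx plus wrap versus placebo plus wrap. The last stays at 5% because no bias was assumed between the wrap arms. The arithmetic is the same whether the shift comes from lack of masking or from a real wrap effect.

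**4. If the two wrap arms are not masked from each other (illustration).** A 0.5-point shift between two arms with no true difference, 16 per arm, two-sided t-test with 30 degrees of freedom: false-positive rate 15.0%, 10.5% and 8.5% at SD 1.5, 2 and 2.5. This is the harm that coded kits would address; step 3 is not.

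**5. Power of the contrast that isolates the foam.** Theraworx plus wrap versus placebo plus wrap, 2-point difference, pooled variance with 45 degrees of freedom, noncentrality 2 / (SD × √(2/16)):

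- SD 1.5: 3.77, power 0.958
- SD 2: 2.83, power 0.790
- SD 3: 1.89, power 0.454

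**6. Predictability of allocation.** Assume fixed blocks of 3, known to the coordinator. If past allocations are known, the last in each of 20 blocks is certain: 20 of 60. With coded kits, the wrap or no-wrap status can still be foreseen. If foam alone comes first in a block (probability 1/3), two allocations are known; otherwise one is. The expectation is 1/3 × 2 + 2/3 × 1 = 4/3 per block, or about 27 of 60.

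**7. Can the wrap arms be masked at all?** Research Activities, item 1, describes the wrap as treated with Theraworx foam and does not separate out the placebo arm. Basic Information, item 3, describes a control with a wrap and mentions no foam. Study Design, item 2, has placebo foam with wrap. A control without foam could not be masked to participants; a matched placebo foam could. The three descriptions do not agree.

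**The case against.** The strongest reply is that the hypotheses in Study Aims already name the comparisons. A shift confined to the foam-alone arm would not support the placebo half of Hypothesis 1a, so a careful reader would not credit the foam on the ANOVA alone. This stands in part: the intent is documented. The SAP does not carry it through, and followed as written it ends with the ANOVA.

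A second reply is that the ANOVA illustration concerns the choice of contrast more than the coordinator's several tasks. That is right. Coded kits would leave the 10% unchanged, which is why the two weaknesses are kept apart here.

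A third is that administering a questionnaire need not mean interviewing, and that participants also record daily pain on their own sheet. The sheet is a partial check on influence through the coordinator. It cannot check the effect of participants knowing whether they have a wrap.

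A reader might infer that the trial is open-label, or that the coordinator knows which foam each wrap participant receives. The documents say neither. Consent pages and the attached data forms are not in the available text and may mention masking, and more than one person may fill the coordinator role.

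**Conclusion.** The point holds as a gap in the described conduct and a mismatch between hypotheses and SAP. Masking and concealment are not described, contrasts with foam alone are unmasked for the participant and for whoever dispenses, and the planned test can be significant with an inert foam.

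A reader might take the 10% as the trial's actual false-positive rate. It is not: both the 0.25 SD shift and the SD are assumptions, and the documents give no basis for the size, or even the presence, of a real bias. Nor can it be said that masking the wrap arms is certain to be feasible, because the descriptions of the control differ.

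This should be changed, but it does not invalidate the trial, which calls itself a pilot. Confidence is medium.

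**What to change.** 1. Have participants complete the pain score and DASH themselves on paper at each visit, before strength and motion testing. Cost: a few minutes of participant time.
2. State in the SAP that the conclusion about the foam rests on Theraworx plus wrap versus placebo plus wrap at 2 weeks, in line with Study Aims, and that a significant three-arm ANOVA alone is not sufficient. Add as a limitation that contrasts with foam alone are unmasked for participants and for the dispensing coordinator. Cost: a short addition to the SAP, and less weight on the foam-alone contrasts. Power for 2 points is about 79% at SD 2, close to the planned 80%, but 45% if the SD is 3.
3. Reconcile the descriptions of the wrap and control in Basic Information, item 3, and Research Activities, item 1, with the three arms in Study Design, item 2. They decide whether the wrap arms can be masked.
4. Then, where a matching placebo container exists or can be prepared, dispense the two foams as coded, numbered kits. The list should be held by someone who does not consent, dispense or assess, with varying block sizes not disclosed to the coordinator or the PI. Cost: labelling and possibly repackaging. The documents describe only the PI and a coordinator in study conduct, so this depends on staff not described. If such a person is available, an assessor not involved in dispensing could also be considered for grip, pinch and motion; since the wrap is worn at night, that assessor could be masked in all three arms.
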